General Study Information

Principal Investigators: [name], Ph.D., [name], Ph.D., [name], Ph.D., and [name], OT, Ph.D.

Study Title: Development of Technologies to Increase In-Seat Movement to Prevent Sitting-Acquired Pressure Injuries in Wheelchair Users: AIM 3 Evaluation

IRB #: 19-008916

Protocol version number and date: Version 9, 09/15/2022

Research Question and Aims

Aims, purpose, or objectives: SPECIFIC AIM 3: Assess the effectiveness of the Sensoria® Mat Wheelchair Wellness Coach (Sensoria® Mat) and Assisted Weight-Shift© (AW-Shift©) systems for changing the movement behavior of wheelchair users who are at risk for pressure injuries.

Hypotheses: A) Individuals will complete more frequent and more consistent weight-shifts with access to the feedback systems compared to baseline. B) Self-efficacy beliefs for completing weight-shifts will increase with use of the feedback systems.

The key to reducing risk is understanding the factors that contribute to pressure injuries, having the technical ability to measure these factors, and using these measurements to impact users and mitigate risk of seating pressure injuries. The successful completion of this project will make large advancements in optimizing feedback about pressure and movement that will help wheelchair users with spinal cord injuries (SCI) become more effective in managing pressure distribution on an ongoing, daily basis.

Background:

A. SIGNIFICANCE: Pressure-related injuries in individuals with SCI are one of the most dangerous secondary health problems encountered throughout the lifespan [1, 2]. With recurrence rates as high as 79% [6-8] and mortality rates as high as 48% when sepsis is present [4, 5], there exists a critical clinical need to target prevention of pressure injuries. **Despite the prevention efforts implemented over the years, pressure injuries continue to occur at a high rate of incidence.** This is true even though the National Pressure injury Advisory Panel estimates that 80% of all pressure injuries are avoidable [14]. New prevention strategies are needed that focus on modifiable risk factors.

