Initial/Baseline Visit: This visit may be completed in-person, or virtually. The subject will receive standard guidelines/education on weight-shift frequency for pressure injury prevention, and may have their skin health reviewed by the study team. Research staff will provide a basic overview of all systems and mobile apps. The WiSAT mat will be installed underneath the participant's wheelchair cushion to monitor in-seat movement, and will remain under the cushion throughout the study. A mobile app associated with the WiSAT mat may also be installed on participants phone, or provided with a separate mobile device. This app will remain in the background and be used to maintain the clock on the WiSAT data logger. Users may open the app to determine if the WiSAT device needs to be charged, but the app will not provide any weight-shift feedback or information. The participant will perform three leans to initialize the WiSAT mat and ensure accurate monitoring,

Baseline Collection: During the 2-week baseline collection, the in-seat movement behavior will be continuously and passively (no interaction required by the participant) measured with the WiSAT mat installed underneath the wheelchair cushion to determine how much movement the participant performs.

Pre-Intervention Phase Calls/Visits: Before each intervention phase, study staff will meet with the participant via phone, video call, or in-person to assist the participant in setting up the correct system for the phase. Study staff will help the participant download the correct mobile app onto their phone. They will be instructed on how to properly fit and secure the correct system to their wheelchair cushion. Participants will be directed to set personal weight-shifting goals within the app that will generate customized weight-shift reminders (or to leave the default setting). Questions regarding use of the intervention will be answered at this time, skin/general health may be assessed, and the WiSAT leans will be performed again. There will be two pre-intervention calls/visits at beginning of weeks 3 and 9.

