Intervention Phases: During the intervention phases, the participants will have full access to their designated system (Sensoria® Mat or AW-Shift©) and data from their interactions with each system will be recorded remotely. No PHI is collected through either system. Participants may be asked to perform regular tasks or weight-shifts throughout the intervention phases. Study staff will be able to see the participant's interactions with the systems and may contact them during this time regarding technical difficulties.

Post-Intervention Phase Calls/Visits: Immediately after each intervention phase, study staff (who are not masked to the participant IDs) will meet with the participant via phone, video call, or in-person to check-in on their skin/general health, and prepare them for the washout phase. They will complete questionnaires by phone,

electronically/via email (REDCap), or they may be mailed a hard copy. There will be two post-intervention calls/visits at the end of weeks 6 and 12.

At the 2nd post-intervention call/visit, the participant will be instructed on how to return the study equipment and study apps will be deactivated/removed from their phone.

Washout Phase: The Sensoria® Mat and AW-Shift© apps are deactivated during the washout phase. The WiSAT mat will continue to passively monitor in-seat movement, and the system used in Intervention Phase 1 will be removed from their wheelchair.

Study Timeline:

	Screening Call	Informed Consent	Baseline Visit	Baseline Collection (2 weeks)	Intervention Phase 1		Washout Phase (2 weeks)	Intervention Phase 2	
					Pre-Intervention Call/Visit	Post-Intervention Call/Visit		Pre-Intervention Call/Visit	Post-Intervention Call/Visit
Visit No.	0	1		2	3		4	5	
Visit Week	-2	0		3	6		9	12	
Allowable window (in days)		±7		±1	±1		±1	±1	
Inclusion/Exclusion	X	X							
Informed Consent*		X*	X*						
Demographics/SCI and Medical History			X+						
Skin/Health Check	X	X+		X	X		X	X	
Pressure Injury/Weight-Shift Guidelines		X							
WiSAT System Installation		X							
Leans for WiSAT Initialization		X		X			X	X	
System Training/Set-Up		X		X				X	
PUK Questionnaire		X+							
SE Questionnaire		X+			X				X
Early Detection and Action: Pressure-Related Concerns Questionnaire			X+		X				X
SUS Questionnaire					X				X
Usability Questions					X				X
Structured Interview Questions					X				X
Return Equipment					X				X

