*Informed consent discussion may occur via phone or Zoom prior to the baseline visit or during the baseline visit (in-person).

+Participants may complete some portions of the baseline study visit during the informed consent call after they have signed the consent form.

Questionnaires: Participants will complete questionnaires at various timepoints during the study. These questionnaires may be sent electronically using REDCap, completed via phone with study staff, or the participant may complete a paper copy.

Pressure Ulcer Knowledge Questionnaire (PUK): A 6-item questionnaire that measures a person's perception of their own pressure ulcer knowledge.

Self-Efficacy (SE) Short Form Questionnaire: A 4-item form addressing common issues related to performing weight-shifts.

Early Detection and Action: Pressure-Related Concerns Questionnaire: A 12-item questionnaire that focuses on awareness and early detection of skin/pressure-related problems.

System Usability Scale (SUS): The System Usability Scale is a 10-item questionnaire with five response options for respondents. This questionnaire will be administered after each intervention period.

Usability Questions: A 14-item form addressing specific usability questions with regards to the intervention systems.

Structured Interview Questions: After each intervention phase, participants may be asked structured interview questions regarding the seating system.

Study Equipment: Equipment for the WiSAT system, Sensoria® Mat, and AW-Shift© may be given to participants via mail or in-person at study visits. Participants will be provided with adequate mailing supplies and instructions on how to return the equipment.

Participant Tech Support: To provide timely and efficient technological support to study participants while using the seating pressure systems, we may send text messages at regular intervals throughout the study to check-in on the function of the systems. We will use an approved service/method of sending these communications, and none of these messages will contain PHI. Only participants who have given specific permission will receive these text messages.

Primary Outcome Measure:

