Change in in-seat movement between baseline and intervention: The difference in average weight-shift frequencies per hour of wheelchair occupancy between the baseline phase and the intervention phases will be calculated to determine if having an intervention increased in-seat movement. Weight-shifts will be measured by the WiSAT mat, where a weight-shift is defined as a partial unloading lasting more than 15 seconds, and a pressure relief is a specific weight-shift that completely unloads the buttocks for more than 15 seconds. The number of weight-shifts is calculated for each day as the number of events divided by the number of hours spent in the wheelchair. The daily values are averaged across days with at least 4 hours of wheelchair occupancy to define the value for the study phase.

Secondary Outcome Measures:

Self-efficacy: A self-efficacy for weight-shift performance scale is being developed and psychometrically tested as part of related study at Mayo Clinic. Development of this scale follows Albert Bandura's guidelines for creating self-efficacy scales [84]. Items are self-scored by the participant on a scale of 0-100. Item analysis will allow comparison of the different compensatory techniques across the various sub-tasks related to shifting weight or moving more frequently. This level of analysis may allow clinicians to eventually screen individuals for specific challenges and, based on areas where self-efficacy is low, recommend the most appropriate type of compensatory strategy. Self-efficacy is assessed during the baseline visit, during each post-intervention video call, and during the follow-up visit.

Comparison of systems: The difference in average weight-shift and pressure relief frequencies per hour of wheelchair occupancy between the baseline phase and the intervention phases will be calculated and compared across the systems to determine whether there is a difference across systems' effectiveness.

Change in consistency/distribution of weight-shifts: Consistency of weight-shifts is measured by two metrics of the distribution of weight-shifts across a day: 1) The longest daily duration the participant is seated without performing a weight-shift, and 2) The coefficient of variation of the time between weight-shifts. An effective system will reduce the longest daily duration without a weight-shift, and may reduce the coefficient of variation of time between weight-shifts.

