Covariates/Confounding Variables: For all outcome measures, the effect of **relevant biological variables** including **sex, age**, and pressure injury history will be assessed as covariates in the analysis. Additionally, wheelchair type and level of sensation will be included in the covariate space. Randomization will be blocked by site to reduce any confounding effects of study site. Variables will be transformed as necessary to meet appropriate distributional assumptions for modeling (e.g. normality).

SA3a Hypothesis: Individuals will complete more frequent and more consistent weight-shifts with access to the feedback systems compared to baseline: The change in-seat movement frequency (weight-shifts/hour) and consistency (max and COV of time between weight-shifts) between baseline and interventions will be analyzed using a mixed effect model with fixed effects for treatment and time trend, and mixed effects for subject and time trend within subject. Movement during the washout periods will be adjusted for in the analysis if during washout, the participants do not return back to their baseline movement level.

SA3b Hypothesis: Self-efficacy beliefs for completing weight-shifts will increase with use of the feedback systems: The change in self-efficacy will be analyzed using a mixed effect model as described in SA3a Hyp.

Other Outcome Measures: The difference in effectiveness between systems (interventions) will be analyzed using a mixed effect model as described in SA3a Hyp. The QUEST and SWLS questionnaire and mobile app interaction results will be analyzed using repeated measures ANOVA to determine if there are differences across intervention phases.

Missing Outcome Data: The primary outcome measure is collected passively with no need for the participant to interact with the system (no battery charging needed during this phase). The questionnaires are collected via phone/video call, so we are not relying on returned paper copies. Mixed models handle missing data naturally, so that all available data points may be analyzed, irrespective of whether the subject had some outcome data missing. However, analyses of data with multiple imputation for missing data may be attempted, if the data are likely to be missing at random.

References

1. Krause, J.S., *Skin sores after spinal cord injury: Relationship to life adjustment*. Spinal Cord, 1998. **36**(1): p. 51-6.

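### The only pre-intervention self-efficacy reading may precede the weight-shift education, so SA3b can credit an education gain to the feedback systems

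*Combined protocol and SAP*

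**What the plan says.** Hypothesis B (Research Question and Aims) is that "Self-efficacy beliefs for completing weight-shifts will increase with use of the feedback systems". Under Data Analysis, Endpoints, the secondary endpoint is the SE change from baseline to the interventions. The SA3b paragraph says "The change in self-efficacy will be analyzed using a mixed effect model as described in SA3a Hyp", meaning fixed effects for treatment and time trend, with subject and subject-by-time effects.

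On timing:

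- In the Study Timeline, the row "SE Questionnaire" has X+ at consent/baseline and X at the two post-intervention contacts (weeks 6 and 12). No SE form falls at the week 3 or week 9 pre-intervention contacts.
- The plus footnote reads "Participants may complete some portions of the baseline study visit during the informed consent call after they have signed the consent form". The asterisk footnote allows the call to come first: "Informed consent discussion may occur via phone or Zoom prior to the baseline visit or during the baseline visit (in-person".
- The education row (pressure injury and weight-shift guidelines) has a plain X. The Initial/Baseline Visit paragraph places it there: "The subject will receive standard guidelines/education on weight-shift frequency for pressure injury prevention". That paragraph does not say whether the SE form comes before or after.
- Secondary Outcome Measures, Self-efficacy, says: "Self-efficacy is assessed during the baseline visit, during each post-intervention video call, and during the follow-up visit". The timeline contains no follow-up visit.
- Baseline Collection records movement for two weeks after the baseline visit, so after the education.
- The washout adjustment in the SA3a paragraph is triggered by movement not returning to its baseline level. The Exploratory Outcome Measure paragraph acknowledges that no arm goes without a compensatory strategy.

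**The concern.** Education on how often to shift weight could plausibly change a person's confidence in doing weight-shifts, whatever device follows. If the SE reference is taken before that education, the change to week 6 or week 12 is education plus system, while Hypothesis B speaks only of the systems. Movement is better protected, because its reference period follows the education. SE uses the same model without that protection, and no later reading before phase 1 could replace the early one. A positive SA3b result could then arise with systems that do nothing for self-efficacy.

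A second gap concerns phase 2. Without an SE value at the end of washout, nobody can tell whether SE had returned to its starting level before the second system was introduced.

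**Working it through.** The plan gives no figure for SE variability or SE power, so there is no SE figure to reproduce. The analysable sample size does reproduce: 48/(1 - 0.20) = 60 recruited.

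**1. Where an education gain goes in the planned model.** Code the three scheduled SE readings as time 0, 1, 2, with both sequences equally represented. Averaged over sequences, with intercept a, pooled system effect T and slope s:

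- pre = a
- post1 = a + T + s
- post2 = a + T + 2s

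Solving, s = post2 - post1 and T = 2×post1 - pre - post2. A lasting education gain d in people who answered before the education gives readings 0, d, d. Then s = d - d = 0 and T = 2d - 0 - d = d. The whole gain goes to treatment and none to the trend. Dropping the trend also gives T = d. Fitting the two systems separately by generalised least squares gives d on each.

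**2. Can education be separated from treatment?** The design matrix with intercept, treatment, time and a post-education step has rank 3 of 4 at weeks 0, 6 and 12, so it cannot. With readings added at weeks 3 and 9 the rank is 4 of 4, so it can. Participants on the abbreviated design have two scheduled readings; within them treatment and trend are themselves aliased.

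**3. Size.** Assumptions, none from the documents: within-person change SD of 15, 20 or 25 points on the 0-100 scale; exchangeable errors; normal approximation; systems with no effect; a gain d that lasts to week 12; every participant answering before the education. From the plan: n=48, two-sided 0.05.

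- Simple paired contrast: standard error = SD/√48 = 2.165, 2.887, 3.608.
- With the trend: the variance of 2×post1 - pre - post2 is 6σ² per person, against 2σ² for one paired change. The standard error is therefore √3 times larger: 3.75, 5.00, 6.25.
- Probability of significance = Φ(d/se - 1.96) + Φ(-d/se - 1.96).

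| Mean gain d | Model | SD 15 | SD 20 | SD 25 |
|---|---|---|---|---|
| 5 | with trend | 27% | 17% | 13% |
| 10 | with trend | 76% | 52% | 36% |
| 5 | paired, no trend | 64% | 41% | 28% |
| 10 | paired, no trend | 99.6% | 93% | 79% |
| 2.5 (half answer first, gain 5) | with trend | 10% | 8% | 7% |

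The with-trend rows match the planned model. The paired rows show what happens if the trend is dropped. The last row takes half of a 5-point gain as the mean shift.

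**4. Carry-over.** Suppose one system raises SE by 10, the other by 0, and the gain fully persists. The sequences read 0, 10, 10 (active first) and 0, 0, 10 (inert first). With system A, system B and a linear trend under exchangeable errors, the estimates are +2.5 for the active system, -2.5 for the inert one and a slope of 5. The true difference of 10 appears as 5. Without the trend the estimates are 10 and 5, again a difference of 5.

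**The case against.** The plus footnote is permissive, and the Self-efficacy paragraph places the reading during the baseline visit. Some or most participants may answer there, possibly after the education. That stands: the bias is possible, not certain, and shrinks with the share who answer first. It does not remove the point, because the order within the visit is not fixed either. The flattened timeline does not explain it away: the plus sign itself distinguishes the two rows, and the Initial/Baseline Visit text places the education independently.

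No document figure supports a gain of 5 or 10 points, or its persistence. The education is standard guidance, and recruitment includes earlier aims of this project, so some participants may already know the content. This also stands; the rates are illustrations under stated assumptions. The contrast with movement should not be pushed too far: a decaying education effect could still touch the two-week movement baseline.

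A reader might infer that phase-1 carry-over is likewise a false credit under Hypothesis B. The documents do not support that. The hypothesis concerns the feedback systems together, and belief persisting from phase 1 is itself a system effect. With the planned trend, a carry-over pattern 0, 0, c gives T = -c and s = c, lowering the system-versus-baseline estimate. What remains is that SE carry-over can be neither detected nor adjusted, which matters when systems are compared.

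Finally, SE is a secondary endpoint, and attribution limits come with any pre-post design. True, but this one is avoidable at contacts that already exist.

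**Conclusion.** The point holds as a scheduling weakness that can bias SA3b. Any lasting education gain among participants who answer SE first enters the system-versus-baseline estimate in full, and no analysis of the scheduled readings alone can separate it from treatment. Under the assumptions in the working, with the planned trend, the chance of a significant result from inert systems is about 13-27% for a 5-point gain and 36-76% for 10 points, against 5%. It falls to about 7-10% for 5 points if half answer first. The documents do not show how many will answer first or how large the gain is, so they do not support saying that SA3b will be biased, only that the schedule allows it.

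Separately, unmeasured SE carry-over can halve a true between-system difference of 10 to about 5 if it persists fully. The Self-efficacy paragraph and the timeline also disagree about a follow-up reading.

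**What to change.** 1. Add the four-item SE form at the first pre-intervention contact (beginning of week 3), before system set-up, and define SA3b change from that reading.
2. Add it at the second pre-intervention contact (beginning of week 9), so that SE carry-over can be assessed and the second phase has its own pre-phase value.
3. Reconcile the follow-up visit in the Self-efficacy paragraph with the timeline. The text does not indicate that it was meant as a week 9 reading, and a follow-up reading would not supply a pre-phase value.
4. For participants already past week 3, use recorded completion dates, whether from REDCap, phone or paper, to identify SE forms completed before the baseline visit. Repeat SA3b without them as a sensitivity analysis, or state that for them SA3b estimates education plus system. Forms completed at the baseline visit remain ambiguous unless the order was recorded.

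Cost: four extra items at each of two existing contacts and a minor amendment to the schedule and the SA3b paragraph. No new visit is needed.

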Recording identifiers (including a code) during the conduct of the study allows you to return to the medical record or data source to delete duplicate subjects, check a missing or questionable entry, add new data points, etc. De-identified data is medical information that has been stripped of all HIPAA identifiers so that it cannot be linked back to the subject. De-identified data is **rarely** used in the conduct of a research study involving a chart review.

Review the list of subject identifiers below and, if applicable, check the box next to each HIPAA identifier being recorded at the time of data collection or abstraction. Identifiers apply to any subject enrolled in the study including Mayo Clinic staff, patients and their relatives and household members.

Internal refers to the subject's identifier that will be recorded at Mayo Clinic by the study staff.

External refers to the subject's identifier that will be shared outside of Mayo Clinic.

Check all that apply:	INTERNAL	EXTERNAL
Name	X	X
Mayo Clinic medical record or patient registration number, lab accession, specimen or radiologic image number	X	X
Subject ID, subject code or any other person-specific unique identifying number, characteristic or code that can link the subject to their medical data	X	X

Dates: All elements of dates [month, day, and year] directly related to an individual, their birth date, date of death, date of diagnosis, etc.	X	X
Note: Recording a year only is not a unique identifier.		
Social Security number		
Medical device identifiers and serial numbers		
Biometric identifiers, including finger and voice prints, full face photographic images and any comparable images	X	X
Web Universal Resource Locators (URLs), Internet Protocol (IP) address numbers, email address	X	X
Street address, city, county, precinct, zip code, and their equivalent geocodes	X	X
Phone or fax numbers	X	X
Account, member, certificate or professional license numbers, health beneficiary numbers		
Vehicle identifiers and serial numbers, including license plate numbers		
Check 'None' when none of the identifiers listed above will be recorded, maintained, or shared during the conduct of this study. (exempt category 4)	 None	 None

Data Analysis

Endpoints:

Primary: The primary endpoint will be the change in in-seat movement frequency (weight-shifts/hour) and consistency (max and COV of time between weight-shifts) between baseline and interventions.

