Secondary: The secondary endpoint will be the change in self-efficacy between baseline and interventions.

Tertiary: The tertiary endpoint will be the difference in effectiveness between systems (interventions).

Power Statement: This aim is powered based on the primary outcome measure of in-seat movement behavior, quantified as the change in weight-shifts per hour from baseline to during the use of an intervention. A clinically meaningful change in movement (~50% increase) was defined by preliminary data from the WiSAT system. The data will be analyzed using a mixed effect model with fixed effects for treatment and time trend, and mixed effects for subject and time trend within subject. Power calculations were estimated via simulation. Various scenarios defined by sample size, effect sizes and variances (for error and random effects) were inspected by creating 1000 simulated data sets for each scenario. The response was assumed to be log-normally distributed, with log-transformations employed for modeling. Power was estimated using the percentage of simulated data sets returning a significant result for the hypothesis of interest. All tests are 2-sided with a 0.05 Type I error rate. Table 1 shows the results using a standard deviation of 0.35 (for the log-response), and 0.8 and 0.2 for the random effects of subject and time-subject. Forty-eight subjects will achieve 97% power to detect a 50% increase in weight-shifts and 100% power to detect a 100% increase regardless of sample size (Table 1), as well as sufficient power to detect differences between the 2 interventions (Table 1). Sample size below 48 participants does not allow for sufficient power to detect intervention vs. intervention differences. To accommodate 20% attrition, a total of 60 participants will be recruited into the study.

Sample Size	Intervention vs Baseline			Intervention vs Intervention		
	25% ↑	50% ↑	100% ↑	0% vs 50%	25% vs 50%	50% vs 100%
48	55%	97%	>99%	>99%	67%	96%
54	61%	98%	>99%	>99%	71%	97%
60	66%	99%	>99%	>99%	78%	98%

Table 1. Statistical power at 0.05 significance level for varying sample sizes at standard deviation (error)=0.35

Data Analysis Plan: Interim monitoring and early stopping rules are documented in the Data Safety and Monitoring Plan. The statistician will be masked to the intervention type during data analysis. All tests are 2-sided with a 0.05 Type I error rate. Analysis will be conducted with SAS and R software.

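### The plan defines the primary endpoint in two ways (frequency alone, or frequency with longest gap and COV) and gives no rule for what counts as success

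*Combined protocol and SAP*

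**What the plan says.** **Methods.** Primary Outcome Measure contains one quantity: "The difference in average weight-shift frequencies per hour of wheelchair occupancy between the baseline phase and the intervention phases will be calculated", and the stated purpose is "to determine if having an intervention increased in-seat movement". Consistency comes under Secondary Outcome Measures: "Consistency of weight-shifts is measured by two metrics of the distribution of weight-shifts across a day", namely the longest daily spell seated without a weight-shift and the COV of the time between shifts. An effective system is expected to shorten the longest spell, "and may reduce the coefficient of variation of time between weight-shifts".

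**Data Analysis, Endpoints.** "The primary endpoint will be the change in in-seat movement frequency (weight-shifts/hour) and consistency (max and COV of time between weight-shifts". The next tier is "The secondary endpoint will be the change in self-efficacy between baseline and interventions", so consistency has no secondary place in this list.

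**Power Statement.** The calculation concerns weight-shifts per hour only: 97% power for a 50% increase with 48 participants, and 60 recruited to allow for 20% attrition.

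**Data Analysis Plan and SA3a Hypothesis.** Every test is two-sided at 0.05. SA3a puts frequency, max and COV through the same type of mixed model and ranks none of them.

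The between-system comparison also changes tier. It is a secondary outcome in Methods ("calculated and compared across the systems to determine whether there is a difference"), while Endpoints says "The tertiary endpoint will be the difference in effectiveness between systems (interventions". That is a minor labelling mismatch.

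**The concern.** Both definitions stand in the current text and they cannot both hold. The plan also lacks the rule that would make the difference harmless. It does not say whether one successful metric is enough or all three are needed. Nor does it say whether success means either system beating baseline, both doing so, or a pooled intervention effect.

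The consequence depends on the missing rule. If any one metric is enough, the error rate of the primary claim is above the nominal level. If all three are needed, the error rate is safe but the power statement describes a different claim. With the rule unwritten, whether longest gap and COV count towards the primary claim can be settled after the results are seen.

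**Working it through.** **1. What the 97% refers to.** Inputs from the Power Statement: error SD 0.35 on the log scale, random effects 0.8 (subject) and 0.2 (time within subject), both read as SDs, and n = 48. A 50% increase is log(1.5) = 0.4055. The time coding is not given. I assumed one value per phase in a two-sequence crossover with a linear trend.

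- Phases at 0, 0.58, 1.58 (six-week units): SE 0.106 for one system against baseline on frequency. Power = Φ(0.4055/0.1061 − 1.96) = 96.9%. The five Table 1 columns checked agree within 2 points at n = 48, 54 and 60.
- Phases at 0, 1, 3: SE 0.103 and power 97.6%, but 60% for 25% vs 50%, where Table 1 has 67%.
- Phases at 0, 1, 2: power 88.0%, which does not match.
- Attrition: 48/0.8 = 60, as stated.

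The 97% is therefore reproduced as the power of one frequency contrast. Longest gap and COV play no part in it.

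**2. If any one of the three metrics is enough (one contrast, each test two-sided 0.05).** With independent metrics, familywise error = 1 − 0.95³ = 14.3%. Hypothesis A is directional, so the rate of false claims of improvement is 1 − 0.975³ = 7.3%, against 2.5% for a single test. The documents give no between-metric correlation. A multivariate-normal simulation over assumed values gives:

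| Assumed correlation | Any false positive (nominal 5%) | False claim of improvement (nominal 2.5%) |
|---|---|---|
| 0 | 14.3% | 7.3% |
| 0.8 | 9.8% | 4.9% |
| 0.9 | 8.4% | 4.2% |

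**3. If all three must succeed.** There is no inflation. Power cannot be computed, because no effect size or SD is given for longest gap or COV. For illustration only, with independent metrics: if each of the other two also had 97% power, joint power would be 0.97³ = 91%. If each had 80%, it would be 0.97 × 0.80 × 0.80 = 62%.

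**4. What each rule for the two systems costs once frequency alone is primary (n = 48).** Back-solving Table 1:

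- SE against baseline = 0.4055/(1.96 + 1.881) = 0.1056 from the 50% column, or 0.2231/(1.96 + 0.126) = 0.107 from the 25% column.
- SE between systems = 0.1823/(1.96 + 0.440) = 0.076.
- Correlation of the two contrasts = 1 − 0.076²/(2 × 0.107²) = 0.75.

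Results for a 50% increase, with ranges covering the back-solved SEs and the 0, 1, 3 coding:

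- *Holm, one given system at the first step:* Φ(0.4055/0.1056 − 2.241) = 94.5%; range about 94-95.5%.
- *Holm, at least one system succeeds when both work:* about 97.5-98%.
- *Both must succeed, each at 0.05:* about 95-96%.
- *Pooled contrast:* SE = 0.107 × √(1.75/2) = 0.100. If both systems work, Φ(0.4055/0.100 − 1.96) = 98%, range 98-99%. If one system does nothing the pooled effect halves: Φ(0.2027/0.100 − 1.96) = 53%, range 53-57%.

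**The case against.** **Frequency is never in doubt.** It is primary in Methods, in Endpoints and in the Power Statement, and Missing Outcome Data refers to the primary outcome measure in the singular. This stands. A reader might infer that any of several results could be chosen as primary. The documents support only the narrower point that longest gap and COV are in one definition and out of the other.

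**Hypothesis A may already require everything.** It predicts more frequent and more consistent shifts, which could mean that all metrics must succeed. But it is a hypothesis, not a decision rule, and the weak expectation for COV in Methods sits poorly with making COV compulsory. If that reading is intended, the power statement does not cover it.

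**A wrong-direction result cannot support a directional hypothesis.** This is correct. A reader might infer that the chance of a false claim of improvement exceeds 5%. At correlations of 0.8 to 0.9 it does not. The right benchmark for that rate is 2.5%, and it is exceeded at every correlation tried.

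**The plan points to one contrast per system.** Study Design compares baseline with two intervention phases, and Table 1 allows the systems to differ. This is fair indirect evidence, but not a rule. With phases at 0, 0.67, 1.67, a pooled contrast gives 97.4% at n = 48, so Table 1 alone cannot settle it.

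**Conclusion.** The conflict is real and needs correcting, because two incompatible definitions of the primary endpoint stand in the current text and no success rule resolves them. If any one of the three metrics is enough, two-sided familywise error for one contrast is about 8-14% instead of 5%, or about 4-7% instead of 2.5% for false claims of improvement. These ranges rest on assumed between-metric correlations of 0.9 to 0. If all three are required, error is controlled and the 97% does not describe the primary claim.

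Two stronger readings are not supported. A reader might count three metrics by two systems as six tests and quote 1 − 0.95⁶ = 26.5%. That needs independence and two unwritten rules at once: that any metric is enough, and that either system is enough. A reader might also infer that 60 participants are too few. The sample size is not shown to be wrong for frequency: splitting alpha six ways would still leave about 88.5% power for a 50% increase at n = 48. The power figures depend on the assumed time coding.

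**What to change.** 1. In Endpoints and SA3a, make weight-shifts per hour the single primary endpoint, as Primary Outcome Measure and the Power Statement already do. List longest daily gap and COV as secondary.
2. In SA3a, state whether the primary test is one contrast per system or one pooled contrast. If per system, use Holm when success on either supports the claim, or test each at 0.05 when both must succeed. A pooled contrast is tested at 0.05.
3. If all three metrics are meant to be required, say so as the success rule and add effect sizes, SDs and power for longest gap and COV.
4. Date the amendment before outcome data are analysed. Study Design refers to participants already enrolled, so this is a mid-trial change.
5. Give the between-system comparison one tier in both sections (minor).

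**Cost.** The change is to wording, with no added participants, but it is not free. Consistency loses primary status, so the primary claim covers only the frequency half of Hypothesis A. Holm lowers first-step power for a given system by about 2-3 points, with essentially no loss in the chance that at least one succeeds when both work. Requiring both costs about 1-2 points against the stated 97%. A pooled test costs no alpha, but it is weak if one system has no effect and supports no claim for either system alone.
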